**Statistical methods:**  
Continuous variables will be summarized in tables and will include the number of subjects, mean, standard deviation (SD), median, minimum, maximum, first (Q1) and third (Q3) quartiles. Categorical variables will be presented in tables as frequencies and percentages.

**Molecular Signature Changes Analyses:**  
A Mixed Effect Model Repeated Measurement (MMRM) will be used to detect any overall differences in the treatment effect at Week 12 compared to baseline in the molecular measurements. This formulation

[figure not shown]
Name of Sponsor/Company:	Name of Investigational Product:	Name of Active Ingredient:
LEO Pharma A/S	Delgocitinib cream 20 mg/g	Delgocitinib
intrinsically models the within patient correlation structure as in the case of a paired t-test. This approach introduces less bias than restricting the analysis for those patients who completed the trial. Time points (baseline, Week 12), treatment group (active, vehicle, and healthy), and tissue (lesional and non-lesional) will be considered as fixed factors, while participant ID will be included as random factor.		
Safety Analyses:  Safety data will be summarized descriptively per cohort. No missing data will be imputed, and no inferential statistics are planned. For Cohort 1, the safety analysis will include reported AEs, including TEAEs, and other safety information (ie. clinical laboratory evaluations and vital signs). For Cohort 2, the safety analysis will include reported procedural complications.		
Efficacy Analyses:  The comparison between the groups for the exploratory efficacy endpoints involving change from baseline will be done using a MMRM, where the absolute change from baseline will be the dependent variable; the treatment group, the visit, and an interaction term for the treatment-by-visit will be the fixed effects; and the baseline value will be the covariate.  The other efficacy endpoints involving proportions of pruritus NRS, burning sensation NRS, and pain NRS will be analyzed using a Chi-square test.		
Sample Size Consideration:  From Del Duca et al. (2020) paper  , the difference in log2-fold changes (SD*) between FFA patients and healthy controls are reported to 4.851 (4.411), 5.298 (5.512) and 4.559 (4.891) for CXCL9, CXCL10 and IFN- $\gamma$ , respectively.  A sample 30 subjects are randomized in an equal manner (1:1) to delgocitinib cream 20 mg/g or vehicle cream. It is expected that a reduction of at least 90% from baseline to Week 12 for the delgocitinib cream 20 mg/g treated subjects compared to only 5% in the vehicle group, normalized to healthy controls, will be observed.  With the above assumptions, the trial should have at least 80% disjunctive power, i.e. a statistically significant difference (tested at 5% one-sided level in an independent two-sample t-test) can be shown with at least 80% probability, in at least one of the genes, assuming no correlation between the tests and same level of variation as reported in the Del Duca et al. (2020) paper  .		
*Derived from the reported p-values coming from a t-test comparing lesional FFA biopsy data (N=12) to data from healthy controls (N=8).		

## 1.2 Trial Diagram

**Figure 1: Trial Diagram**

[figure not shown]
Cohort 1 and Cohort 2 can be conducted in parallel.

### Cohort 1:

Abbreviations: BID, twice daily; OLE, open-label extension.

### Cohort 2:

Notes: For Cohort 2 only, screening and skin samples collection on Day 1 can be performed on the same day at the investigator's discretion, if no medication washout is required and the lifestyle considerations are fulfilled. The optional follow-up period will occur 10 to 14 days after Day 1, to remove biopsy sutures, if needed.

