**Table 2: Schedule of Events for Cohort 2 (Healthy Subjects)**

Trial Visits	Screening	Sample Collection Day	Follow-Up (Optional)
	V1	V2	V3
Window (days)	-30 to -1	-	10 to 14 days after Day 1
Informed consent	X		
Demographics	X		
Medical and surgical history	X	X	
Inclusion-exclusion criteria	X	X	
Brief physical examination	X	X	
Vital signs a	X	X	
Skin biopsies collection b		X	
Suture removal (if applicable)			X
Adhesive skin tape strip samples c		X	
Skin microbiome samples d		X	
Concomitant medication	X	X	X
Procedural complications evaluation	X	X	X

Abbreviation: V, visit.

Note: Screening and Day 1 can be performed on the same day (if subjects do not have a washout period for any of the medications or procedures listed in the exclusion criterion or lifestyle considerations) and the scheduled assessments on these two days can be completed only once in this case.

a Including height and weight. Height will be measured only at screening.

b Two skin biopsies (4-mm) that include hair follicles will be collected on healthy skin at similar matched areas of subjects with FFA (ie., 1 from frontal area and 1 from occipital scalp area).

c Skin tape strips will be collected on non-hair bearing healthy skin at a similar matched area of subjects with FFA (ie, on the forehead, as close as possible to the frontal scalp area).

d Two skin swab samples for microbiome analysis will be collected on healthy skin at similar matched areas of subjects with FFA (ie, 1 on frontal scalp area and 1 from occipital scalp area).

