#### Cohort 2:

All subjects will read and sign an ICF prior to any trial-related activities being performed. Subjects who fulfill all of the inclusion criteria and none of the exclusion criteria will be accepted into the trial. After a screening period of no more than 30 days (from Day -30 to Day -1), eligible subjects will be asked to come at the site for skin samples collection. Screening and skin samples collection on Day 1 can be performed on the same day (if subjects do not have a washout period) or on two separate visits, at the investigator's discretion. No investigational product will be administered in Cohort 2. For scheduled trial visits, subjects will come to the site on up to 3 occasions: screening, Day 1, and optional follow-up visit.

The following skin samples will be collected:

- Skin biopsies (n=2):
  - *Day 1*: 2 skin biopsies (4-mm) that include hair follicles will be collected on healthy skin at similar matched areas of subjects with FFA (ie, 1 from frontal scalp area and 1 from occipital scalp area)
- Adhesive tape strips (n=1):
  - *Day 1*: skin tape strips will be collected on non-hair bearing healthy skin at a similar matched area of subjects with FFA (ie, on the forehead, as close as possible to the frontal scalp area).

- Skin swabs for microbiome analysis (n=2):
  - o *Day 1*: 2 skin microbiome samples will be collected on healthy skin at similar matched areas of subjects with FFA (ie, 1 from frontal scalp area and 1 from occipital scalp area).

For Cohort 2 only, safety will be assessed by review of any procedural complications and changes in health observed after skin samples collection.

No interim analysis is planned in this trial.

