### **8.3.1 Skin Biopsies**

The skin will be cleaned, disinfected, and anesthetized before skin biopsies are performed. Sterile gauze will be used to absorb any bleeding. The biopsy sites will be sutured if necessary.

Details about the collection, processing, handling, storage and shipping of biopsy samples will be provided in the laboratory manual.

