## **8.6 Procedural Complications (Cohort 2 Only)**

For subjects in Cohort 2, procedural complications will be reported instead of AEs.

For the purpose of this trial, a procedural complication is defined as any untoward medical event experienced by a subject that has signed an ICF for the trial, such as infection, bleeding, and/or pain, that the investigator believes to be causally related to the trial procedures performed at Day 1 visit or at the optional visit. Subjects will receive appropriate treatment as needed for any procedural complications that arise.

For the purpose of this trial, a serious procedural complication is any untoward medical event related to the trial procedures that has any of the following consequences:

- Results in death
- Is life-threatening
- Requires in-patient hospitalization or prolongation of existing hospitalization
- Results in persistent or significant disability/incapacity

Note: The term “life-threatening” in the definition of “serious” refers to an event in which the subject was at risk of death at the time of the event; it does not refer to an event that hypothetically might have caused death if it were more severe.

Any medical condition that is present prior to the first sample collection on Day 1 will be considered as part of medical history and not reported as a procedural complication. Should a subject experience an event that he believes to be causally related to the trial procedure performed on Day 1 or at the optional follow-up visit (after sample collection), the event will be recorded as a procedural complication. Any procedural complications whether observed by site personnel or reported spontaneously by the subject will be described in the source document and eCRF.

Any serious procedural complication (this refers to any procedural complication that meets one or more of the aforementioned serious criteria) occurring during the trial must be reported on a serious procedural complication form as per the instructions in Section [8.5.7](#).

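### Cohort 2: no check for procedural complications after Day 1 is required for a healthy volunteer who has no sutures to remove

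*Combined protocol and SAP*

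**What the plan says.** For Cohort 2, Section 4.1 (and the Synopsis) states that "safety will be assessed by review of any procedural complications and changes in health observed after skin samples collection". The same section sets the visits: "subjects will come to the site on up to 3 occasions: screening, Day 1, and optional follow-up visit".

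The note to the trial diagram in Section 1.2 gives the timing and purpose of the last of these: "The optional follow-up period will occur 10 to 14 days after Day 1, to remove biopsy sutures, if needed". Each subject has two 4-mm scalp biopsies on Day 1, and Section 8.3.1 says of closure: "The biopsy sites will be sutured if necessary".

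Table 2 has a row "Procedural complications evaluation", marked at screening, at the sample collection day and at the optional follow-up. Suture removal is marked at the optional follow-up only, where applicable.

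Section 8.6 ties a procedural complication to the procedures done on Day 1 or at the optional visit. It adds: "Any medical condition that is present prior to the first sample collection on Day 1 will be considered as part of medical history". It also provides for recording complications that staff observe or that the subject volunteers.

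For analysis, Section 9.2 defines the Cohort 2 safety set as everyone with at least one skin sample. Section 9.3.4.1 summarizes complications by the number of subjects reporting them.

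**The concern.** The complications that Section 8.6 gives as examples are infection, bleeding and pain. Infection would not be expected to show on the day of the biopsy, and bleeding and pain can also come later. A planned look at each subject some days after sampling is what would find them, and for a subject without sutures to remove the plan requires none.

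Two things are at stake. The first is care for healthy volunteers who, according to Section 2.2.2, can expect no benefit beyond the medical evaluation. The second is how the Cohort 2 safety table reads. A subject not contacted after Day 1 and a subject checked and found well would both appear in the safety set with no event, and the table could not tell them apart.

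**Working it through.** The protocol gives no figure on this point to reproduce, so the check is mainly one of setting the sections side by side.

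**Which checks are required, and what each can find**

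| Table 2 time point | Required for all? | What it can capture |
|---|---|---|
| Screening, on an earlier day | Yes | Nothing: under Section 8.6, conditions present before the first Day 1 sample are medical history |
| Day 1 | Yes | Same-day events, provided it is done after the biopsies |
| Follow-up, 10 to 14 days later | No, optional | Delayed events |

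**Timing on Day 1.** No section says that the Day 1 evaluation follows sampling. Section 1.3 gives an order for assessments due at the same nominal time, with investigator assessments ahead of skin samples, which come last. The complications evaluation is not named in that order. When screening and Day 1 are combined, the note to Table 2 lets assessments due on both days be done once. The one required evaluation could then be a single entry with no stated need to come after the biopsies.

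**Other routes.** The non-leading question asked at all visits is in Section 8.5.5, within a section limited to Cohort 1, and Section 8.6 has no counterpart. Cohort 1 subjects also have two 4-mm biopsies on Day 1 but have adverse events collected at every later visit in Table 1. For Cohort 2, what remains after Day 1 is spontaneous reporting.

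**Length of planned observation.** From the Synopsis, the Cohort 2 periods are up to 30 days of screening, 1 day of sampling and up to 14 days of optional follow-up:

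- With the optional visit: 30 + 1 + 14 = 45 days, and 45/7 = 6.4 weeks, which agrees with the stated approximately 6 weeks.
- Without it: 30 + 1 = 31 days, and 31/7 = 4.4 weeks at most, with 0 days of planned observation after the sampling day.

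**Number affected.** Take 5 subjects, so 5 × 2 = 10 biopsies. If k of them attend the optional visit, planned ascertainment of delayed events covers k subjects, while the safety set holds 5. The number without a later check is 5 − k, anywhere from 0 to 5. The documents give neither the number sutured nor the number expected to attend.

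**Illustration under an assumed rate.** The documents give no rate of late complications. Assume a per-subject rate p of 5%, 10% or 20%, with subjects independent and every late event found when a check is made. The chance that planned checks find at least one is 1 − (1 − p)^k:

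| Checked after Day 1 | p = 5% | p = 10% | p = 20% |
|---|---|---|---|
| k = 5 | 23% | 41% | 67% |
| k = 2 | 10% | 19% | 36% |
| k = 0 | 0% | 0% | 0% |

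For example, with k = 5 and p = 10%, 1 − 0.9^5 = 0.41. Even full follow-up of 5 subjects says little about rates. What it changes is whether a late event in a given subject is looked for at all.

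**The case against.** The strongest reply is that the plan does provide for ascertainment. Table 2 puts a complications evaluation on the sampling day for everyone, and Section 8.6 records spontaneous reports. Serious complications follow Section 8.5.7, under which events after completion are reported if the investigator learns of them. The follow-up visit is also not closed to subjects without sutures. The Synopsis, Section 4.1 and Table 2 call it optional without a suture condition, and marking suture removal as applicable only in some cases implies that the visit can take place without it. Only the note in Section 1.2 links the visit to sutures, and its closing condition may qualify the removal and not the visit.

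Most of this stands, and it rules out three stronger readings:

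- A reader might infer that subjects without sutures are never asked about complications. The Day 1 evaluation contradicts that.
- A reader might infer that the plan counts uncontacted subjects as free of complications. No text says so, and the Synopsis states that missing safety data are not imputed. What follows from Section 9.2 is only that they stay in the safety set, where an absent report is ambiguous.
- A reader might treat the screening evaluation as a fault. On an earlier day it can yield nothing, but removing it would change no result.

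It can also be said that Section 4.1 promises only a review of what is observed, not active follow-up for a set period, and that Section 3 has no Cohort 2 complication endpoint. Both are fair. Even so, a review of changes after sampling has little to work on when no contact after the sampling day is required. Consent pages and the laboratory manual were not available, so any wound instructions given to subjects cannot be judged.

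**Conclusion.** The point holds in a limited form: for a Cohort 2 subject without sutures to remove, the protocol requires no ascertainment of procedural complications after Day 1. This does not depend on how the note in Section 1.2 is parsed, because the visit is optional on every reading and no other contact is scheduled.

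The extent is 0 to all of the approximately 5 subjects, depending on suturing and attendance that the documents do not give. The consequence is confined to the welfare of these volunteers and a descriptive safety summary. Cohort 2 receives no investigational product, and neither the randomized comparison nor the primary endpoint is affected. It merits a change because the change is small, not because the trial's conclusions are at risk.

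**What to change.** In Table 2, keep the on-site suture visit optional, but require the procedural complication and concomitant medication review already scheduled for Day 10 to 14 for every Cohort 2 subject, by telephone when no visit is held. Add that the Day 1 complications evaluation is done after sampling, including when screening and Day 1 are combined. Align the wording of Sections 1.2, 4.1 and 8.6 and the Synopsis.

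The cost is at most about 5 short telephone calls and a Table 2 footnote with matching text. No visit or procedure is added, and no treatment or wound care changes.

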## 1.3 Schedule of Events

The screening evaluation will only be performed after the subject has agreed to participate and has signed and dated the ICF. No treatment or trial-related procedures will be initiated before the informed consent is signed. The Day 1 visit must be performed, at the latest, 30 days after the screening visit. For Cohort 2 only (healthy subjects), the sample collections on Day 1 can be performed on the same day as the screening visit or on separate visits as per the schedule of events, at the investigator's discretion.

The screening evaluation will be performed according to the inclusion and exclusion criteria. If the subject fulfills all inclusion criteria and no exclusion criteria, he or she may be included in the trial.

**Table 1** and **Table 2** provide a description of the procedures to be performed at each visit for Cohort 1 and Cohort 2, respectively.

Unless specified otherwise, the trial assessments scheduled during the trial visits must be performed before the IMP application for subjects in Cohort 1. If assessments are scheduled for the same nominal time, then the assessments should occur in the following order:

- Patient-reported outcomes
- Investigator assessments
- Vital signs
- Medical photographs
- Collection of skin samples

**Table 1: Schedule of Events for Cohort 1 (Subjects with FFA)**

Trial Visits	Screening	Treatment Period							Follow-Up	ET
		Vehicle-Controlled				OLE				
		Day 1	Week 4	Week 8	Week 12	Week 16	Week 20	Week 24	Week 26	-
		V1	V2	V3	V4	V5	V6	V7	V8	V9
Window (days)	-30 to -1	-	±2	±2	±2	±4	±4	±4	±4	-
Informed consent	X									
Demographics	X									
Medical and surgical history	X	X								
Inclusion-exclusion criteria	X	X								
Pregnancy test a	X	X	X	X	X	X	X	X	X	X
Clinical laboratory tests (biochemistry and hematology)	X	X	X	X	X	X	X	X		X
TSH and reflex free T4	X									
Serology (HBV [HBsAg, anti-HBc], HCV, HIV)	X									
Electrocardiogram	X									
Complete Physical examination	X				X			X	X	X
Brief Physical examination		X	X	X		X	X			
Vital signs b	X	X	X	X	X	X	X	X	X	X
Identification of a lesional target area on the scalp and of a non lesional area (eg. occipital scalp) c	X	X								

Trial Visits	Screening	Treatment Period							Follow-Up	ET		
		Vehicle-Controlled				OLE						
		Day 1	Week 4	Week 8	Week 12	Week 16	Week 20	Week 24				
	V1	V2	V3	V4	V5	V6	V7	V8	V9	-		
Window (days)	-30 to -1	-	±2	±2	±2	±4	±4	±4	±4	-		
Perifollicular erythema and scale evaluation of the lesional target area	X	X	X	X	X	X	X	X		X		
Pruritus NRS d	X	X	X	X	X	X	X	X		X		
Burning Sensation NRS d	X	X	X	X	X	X	X	X		X		
Pain NRS d	X	X	X	X	X	X	X	X		X		
LPPAI		X	X	X	X	X	X	X		X		
FFASS		X	X	X	X	X	X	X		X		
Hair counts/Trichoscopy		X			X			X		X		
Hair line measurements e		X			X			X		X		
Medical photographs f		X			X			X		X		
Randomization		X										
IMP application at site		X	X	X	X	X	X					
IMP application BID g		X-----X										
IMP distribution		X	X	X	X	X	X					
IMP collection and/or accountability and/or compliance			X	X	X	X	X	X		X		
Subject diary distribution/collection/review	X	X	X	X	X	X	X	X		X		
Local tolerability assessments h		X	X	X	X	X	X	X		X		

Trial Visits	Screening	Treatment Period							Follow-Up	ET		
		Vehicle-Controlled				OLE						
		Day 1	Week 4	Week 8	Week 12	Week 16	Week 20	Week 24				
	V1	V2	V3	V4	V5	V6	V7	V8	V9	-		
Window (days)	-30 to -1	-	±2	±2	±2	±4	±4	±4	±4	-		
Skin biopsies collection i,j		X			X							
Adhesive skin tape strip samples k		X			X							
Skin microbiome samples l		X			X							
Concomitant medication	X	X	X	X	X	X	X	X	X	X		
Adverse events collection	X	X	X	X	X	X	X	X	X	X		

Abbreviations: anti-HBc, antibody to hepatitis B core antigen; BID, twice daily; ET, early termination; FFA, frontal fibrosing alopecia; FFASS, Frontal Fibrosing Alopecia Severity Score; HBV, hepatitis B virus; HBsAg, hepatitis B surface antigen; HCV, hepatitis C virus; HIV, human immunodeficiency virus; IMP, investigational medicinal product; LPPAI, lichen planopilaris activity index; NRS, Numerical Rating Scale; OLE, open-label extension; TSH, thyroid-stimulating hormone; V, visit.

a For female subjects of childbearing potential, serum pregnancy test at screening and urine pregnancy test at other specified visits.

b Including height and weight. Height will be measured only at screening.

c The lesional target area should be treated with the IMP and should be approximately 3 cm x 6 cm (or equivalent). However, a smaller lesional target area can be selected if tape stripping is performed from the same area where trichoscopy/hair counts is performed or if sample is collected adjacent/close to the lesional target area (refer to Section 8.3.2 for details). If needed, two small lesional target areas (totalling approximately the same size) could be selected to allow for skin samples collection.

d Subjects will complete their NRS at home on a daily basis starting approximately 7 days prior to Day 1 and up to Day 8. On Day 1, the NRS will be completed at the site prior to the first IMP application. After Day 8, the NRS will be completed at the site at the specified visits only.

e Hair line measurements of lateral canthus (right and left) to hairline, lower glabellar crease to hair line, top of frontalis muscle to hair line, and mid brow to hair line (right and left).

f Medical photographs of the target area and the entire scalp (including the frontal hair line and right and left hair line areas).

g The morning application will be on site on visit days. Other IMP applications will be done at home. The first application of the OLE (delgocitinib cream 20 mg/g) is on the morning of Week 12, after all efficacy assessments and skin sample collections are completed. The last application of the OLE is the evening prior to the Week 24 visit. No IMP application will be done on the day of the Week 24 visit.

h Local tolerability assessments will be done by subjects. On Day 1 and Week 12, the local tolerability assessment will be done approximately 30 minutes after the IMP application at the site, with a recall period of 30 minutes. At other visits, the subject's local tolerability assessment will be done before the IMP application with a recall period of 7 days (worst over the last 7 days).

Trial Visits	Screening	Treatment Period							Follow-Up	ET		
		Vehicle-Controlled				OLE						
		Day 1	Week 4	Week 8	Week 12	Week 16	Week 20	Week 24				
	V1	V2	V3	V4	V5	V6	V7	V8	V9	-		
Window (days)	-30 to -1	-	±2	±2	±2	±4	±4	±4	±4	-		

i On Day 1, 2 skin biopsies (4-mm) will be collected prior to the first IMP application (1 from a lesional hair follicle within the target area and 1 from a non lesional hair follicle [eg, on the occipital scalp]). On Week 12, 1 skin biopsy (4-mm) will be collected from a hair follicle within the lesional target area (outside the scar of previous biopsies).

j Within 10 to 14 days after biopsy collection, suture may be removed, if needed. An additional visit(s) may be necessary for suture removal only, if suture removal is needed after Day 1 and/or Week 12.

k On Day 1, optional skin tape strips will be collected prior to the first IMP application from lesional skin and from non lesional skin (eg, on the occipital scalp). The lesional skin tape strip should ideally be collected from the target area but can also be collected adjacent/close to the target area, as long as it includes a portion of lesional skin and is treated with the IMP. On Week 12, skin strips will be collected at the same location of the lesional skin. Every effort should be made to collect tape strip samples in all subjects however, adhesive tape strip collection is optional and will be collected per investigator judgement (based on available skin area on the scalp).

l On Day 1, skin swab for microbiome analysis will be collected prior to the first IMP application (1 from the target area [lesional skin] and 1 from an uninvolved occipital scalp area). On Week 12, skin microbiome will be collected at the same location of the lesional skin of the target area.

